2. Feasibility of recruitment, enrollment, retention and adherence with a two-arm pilot RCT (WhatsApp and control). A target retention rate of at least 90% completing the pilot trial is sought. Retention will be measured by the proportion of participants who will remain in the study by the end of the follow-up period. If we are unable to achieve this target, alternative strategies will be considered for the UH3 phase. One of the primary objectives is to estimate the proportion of successful return blood donation for planning the programmatic randomized clinical trial in the UH3 phase.
3. Acceptability will be assessed with quantitative surveys and participant focus groups to understand the opinions and perspectives of acceptability, effectiveness, feasibility and cultural appropriateness of the docu-drama, WhatsApp and control communication interventions.

Secondary Objectives

To design culturally appropriate communication interventions: docu-drama and WhatsApp groups for retaining first-time blood donors using the PRECEDE-PROCEED framework.

To examine intervention-specific increases in knowledge, attitudes, beliefs, motivations, intention, and relatedness as potential mediators of intention to donate among first-time blood donors. Evaluate the reliability of new or modified outcome measurement instruments.

Study Design

The pilot study utilizes a mixed-methods approach to develop a novel docu-drama communication strategy, evaluate the feasibility of a larger pragmatic randomized controlled trial (RCT) of a WhatsApp based communication strategy and assess acceptability of the communication strategy aimed to increase blood donation among first time blood donors within the catchment areas of the SZBC.

There are two communication interventions: docu-drama and WhatsApp. However, because the development of the docu-drama takes more time, it will not be feasible to include the docu-drama intervention in the pilot RCT, recruit 100% participants, follow up for 6-months for the primary outcome and evaluate the secondary outcomes, considering the duration the UG3 phase. Therefore, only the WhatsApp intervention will be piloted in the RCT. The docu-drama intervention will be designed and test-run in preparation for an RCT in the UH3 phase.

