We will consider factors that must be in place to initiate and sustain first time blood donors' attempts at returning to donate blood. These are called predisposing, enabling and reinforcing factors. We will identify these factors through analysis of primary and secondary data, and put them into categories, and rank their importance.

Predisposing factors, which explain first-time blood donors' behaviour regarding subsequent donation efforts, include knowledge, attitudes, cultural beliefs, and readiness to change. Enabling factors, which enable first-time blood donors to act on their beliefs, attitudes, and knowledge, include the availability of policies, assistance, or resources.

Reinforcing factors, which become prominent after a behaviour has been started, promote repetition or persistence of behaviour through the provision of continuing rewards or incentives such as praise or reassurance.

These factors will be identified from previous data on first-time blood donors in Ghana, and the key informant interviews with participants will be drawn from the NBSG staff, community-based blood donation volunteers, blood donors and non-blood donors.

Phase 5: Administrative and Policy Assessment

Identify the administrative and policy factors that influence what can be implemented. The team will evaluate how organizational factors such as policies, procedures, culture and the availability of resources influence what can be implemented by using two approaches to evaluate implementation research outcomes of the interventions. These are the creation of WhatsApp and docu-drama interventions and test-running the interventions.

WhatsApp pilot RCT

A WhatsApp group will be formed for the pilot RCT. There will be one study team member, who will be the content mediator (research assistant), and who will be responsible for sending

weekly messages and clarifications on blood donation for six months. The participants in the WhatsApp group, after the pilot RCT will have a focus group discussion on what worked well and what did not, and provide information on feasibility, acceptability and cultural appropriateness of the intervention. Prior to, and after exposure to the WhatsApp intervention, a pre-, and post-test survey on the theory of planned behaviour constructs and implementation research measures will be conducted.

Docu-drama test-run

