WhatsApp: Participants assigned to the WhatsApp group will receive weekly messages developed by communication specialists aimed to motivate blood donation, be encouraged to discuss their blood donation experiences, and share their own motivations for donating blood in a moderated, closed group over a six-month duration. The moderator will provide guidelines on acceptable use of WhatsApp, including images they can or cannot share. Participants also receive standard NBSG communications for first-time donors (see below). WhatsApp functions both online and offline. When a participant's WhatsApp is offline (i.e. not connected to the internet), the participant can access posted messages received earlier, respond to these posts and post new comments. However, the participant can only receive newly posted messages only when the WhatsApp is connected to the internet (online). Similarly, the participant's posted messages will only be sent when the participant's WhatsApp is back online.

Control: Participants in this group will receive the standard NBSG communications for first-time donors 1) a “thank you” phone call and 2) and a reminder phone call two-weeks prior to the second blood donation eligibility. The second blood donation eligibility is four months after the first donation.

Avoiding intervention contamination: For the docu-drama intervention, only those invited to receive the intervention will be allowed to view the docu-drama in and be part of the discussions to avoid intervention contamination. In addition, the docu-drama viewing will be conducted face-to-face, which will make it impossible for those who are not present to share the content. For the WhatsApp intervention, only those randomly selected to be part of the WhatsApp intervention group would receive the messages and be part of the discussion. Participants will be advised against sharing the contents of the WhatsApp intervention with those who are not in the group to avoid contamination.

As shown in Figure 2, the two interventions, WhatsApp and docu-drama, are expected to lead to sharing of positive experiences, leading to repeat blood donors. However, for these to occur, the project has several assumptions as indicated in black triangles.

[figure not shown]

Figure 5: The Theory of Change: Community-Based Communication Approaches for Blood Donation in Ghana

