A major assumption is that there will be high fidelity of the interventions. We will assess adherence to the interventions as a key element of fidelity (Carroll et al., 2007). Adherence will include subcategories of content, frequency, duration and dose (Carroll et al., 2007). The extent to which the intended content or frequency of WhatsApp and docu-drama are implemented will

represent the degree of implementation fidelity achieved for the two interventions (Carroll et al., 2007; Song et al., 2010).

Study Population

Inclusion Criteria

Docu-drama design

Design workshop participants will be drawn from blood donors, non-blood donors, drama experts, drama actors, and communication professionals. All must be at least 18 years old, consent to participate and understand English.

WhatsApp intervention design

Key informants will be drawn from the NBSG staff, community-based blood donation volunteers, blood donors, and non-blood donors. All must be at least 18 years old, consent to participate, and understand one of English, Twi, or Ga.

Pilot RCT

- At least 18 years-old
- First-time whole blood donor with the SZBC of the NBSG
- Eligible to donate again
- Consent to participate
- Understands one of English, Twi, or Ga
- Have a smart phone
- Have, or be willing to sign up for an active WhatsApp account

Docu-drama test-run

- At least 18 years-old
- First-time whole blood donor with the SZBC of the NBSG
- Eligible to donate again
- Consent to participate
- Understands one of English, Twi, or Ga

Exclusion Criteria

Docu-drama design

Do not meet the above inclusion criteria

WhatsApp intervention design

Do not meet the above inclusion criteria

Pilot RCT

History of more than one lifetime whole blood donation (with any blood centre)

Docu-drama test-run

History of more than one lifetime whole blood donation (with any blood centre)

Outcome measures

Primary Outcome

The primary outcome for the pilot RCT is to estimate the proportion of return blood donation attempts within six months of enrollment for each arm.

Secondary Outcomes

The secondary outcomes are the following measures.

WhatsApp and control

- Blood donation attitudes,
- subjective norms,
- perceived behavioural control,
- intention,
- ease of use of WhatsApp,
- perceived usefulness of WhatsApp.

Docu-drama, WhatsApp and control

- Intention of using the intervention

- Acceptability of the intervention
- Feasibility of the intervention
- Cultural appropriateness of the intervention

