Cultural appropriateness is the perceived fit, relevance, or compatibility of an intervention; and/or perceived fit of these interventions for promoting blood donation among first-time blood donors (Weiner et al., 2017). Cultural appropriateness will be measured with a five-item questionnaire.

Feasibility is defined as the extent to which an intervention, can be successfully used by the NBSG to promote blood donation among first-time blood donors. Feasibility will be measured with a six-item questionnaire by integrating appropriateness measures (Weiner et al., 2017) and the role of culture as it pertains to health communication (Kreuter & McClure, 2004).

The extent to which respondents participated in the activities will also be documented for the WhatsApp intervention and includes not leaving the WhatsApp group during the intervention; evidence of having read a post, an indicator that can be used in closed WhatsApp groups such as the one to be implemented in the study, and posting at least once a month. Those not reading 50% of the weekly post by the moderator and not posting at least three times during the intervention will be considered as non-adherent. The WhatsApp group moderator will obtain participation data by checking the read status and post by participants.

6–12 months

The second follow-up will involve facilitator-led participant focus group (8 participants per group) discussions of views on acceptability, effectiveness, feasibility, and cultural appropriateness.

The participants involved in the test-run of the docu-drama will be surveyed after the docu-drama with all follow-up instruments (except blood donation attempts) and participate in facilitator-led focus-groups similar to participants in the pilot RCT.

All the constructs will be constructed using a 5-point Likert scale ranging from “completely disagree” to “completely agree”. Focus group discussions will also be held with 6–8 participants from each group to assess all the above implementation research outcomes of interventions.

Risk/Benefit Assessment

Known Potential Risks

Potential risks may include breach of confidentiality and any discomfort that may result from discussions of the docu-drama or issues about blood donation. However, these risks are minimal and are not more than those encountered in everyday life.

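### The WhatsApp non-adherence cut-off requires reading and posting both to fail and ignores leaving, so a donor who posts three times in week 1 and then leaves is not non-adherent

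*Combined protocol and SAP*

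**What the plan says.** Under the 6 months heading of the follow-up assessments, the protocol first lists what will be documented about WhatsApp participation. The list "includes not leaving the WhatsApp group during the intervention", evidence of having read a post, and posting at least monthly. The next sentence sets the cut-off. It labels as non-adherent "Those not reading 50% of the weekly post by the moderator and not posting at least three times during the intervention". The data source follows: "The WhatsApp group moderator will obtain participation data by checking the read status and post by participants".

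Four other places bear on the rule:

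- The fidelity text in Study Interventions: "Adherence will include subcategories of content, frequency, duration and dose".
- The dose. The WhatsApp pilot RCT section has the moderator sending "weekly messages and clarifications on blood donation for six months", and Study Interventions places this "in a moderated, closed group over a six-month duration".
- Primary Objectives, item 2, names "Feasibility of recruitment, enrollment, retention and adherence with a two-arm pilot RCT". The only numerical target there is for retention: "A target retention rate of at least 90% completing the pilot trial is sought".
- The Docu-drama test-run section defines adherence for the other intervention as attending, watching both episodes and staying for the discussion, so every component is required.

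Under Analysis pilot trial, adherence is to be described alongside enrollment and retention. No other WhatsApp cut-off appears in the document.

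**The concern.** The two limbs share one subject and are joined by *and*. Taken literally, failing one limb is never enough, and leaving the group never triggers the label. Yet the sentence just before treats staying in the group as part of participation, and the fidelity text counts duration and dose as part of adherence.

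Adherence is one of three measures by which feasibility of the larger trial will be described. Retention will not pick up the same problem, because it is defined as remaining in the study to the end of follow-up. A donor who leaves the WhatsApp group in week 1 but takes the month 6 call counts as retained and can also escape the non-adherent label. The planners of the larger trial could then see two reassuring figures for someone who received almost none of the intervention.

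**Working it through.** There is no stated figure to reproduce; the check concerns the logic of the rule.

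**Inputs.** The 6-month visit window in Table 1 is days 176 to 190, with midpoint (176 + 190)/2 = 183. Weekly messages give 183/7 = 26.1, so about 26 moderator posts, and 50% of 26 = 13. If the series is instead 24 posts (an assumption, six four-week months), 50% = 12.

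**Rule as written.** Non-adherent = (reads fewer than 13) and (posts fewer than 3). The alternative reading is: non-adherent = (reads fewer than 13) or (posts fewer than 3).

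| Donor (26 weekly posts) | Reads ≥13 | Posts ≥3 | As written (fails both) | Fails either |
|---|---|---|---|---|
| 3 posts in week 1, reads 1, leaves | no | yes | not flagged | non-adherent |
| Reads 0, posts 3, stays | no | yes | not flagged | non-adherent |
| Reads 26, posts 0, stays | yes | no | not flagged | non-adherent |
| Reads 13, posts 0, leaves in week 13 | yes | no | not flagged | non-adherent |
| Reads 1, posts 2, leaves | no | no | non-adherent | non-adherent |
| Reads 26, posts 6, stays | yes | yes | not flagged | not flagged |

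The classifications of these donors are the same with 24 posts. The week-1 leaver has read about 1/26 = 3.8% (1/24 = 4.2%) of the series against the 50% named in the rule, and is not flagged.

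**Direction.** Let r be the share reading at least half, p the share posting at least three times, and b the share doing both. Then:

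- share flagged as written = 1 − (r + p − b)
- share flagged if either failure counts = 1 − b
- difference = (1 − b) − [1 − (r + p − b)] = r + p − 2b

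Because b cannot exceed r or p, the difference is never negative. The written rule always flags the fewest donors that the two limbs allow. The difference is zero only when the same donors meet both limbs. The documents give none of r, p or b, so no value can be put on it.

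**Internal consistency.** Posting at least monthly over six months implies about 6 posts; the cut-off asks for 3 in total. The cut-off is therefore looser than the participation list on posting as well as on staying.

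**The case against.** The strongest reply is that *and* may be deliberate. The intervention is weekly messages plus encouragement to discuss. A rule that reserves the label for donors who neither read nor post is lenient but coherent. A donor who silently reads all 26 messages has received the moderated content, and calling that donor non-adherent is open to dispute. This stands. A reader might infer that the authors meant *or* and that the sentence is a slip, but nothing in the protocol settles that, so replacing *and* with *or* outright would be a preference and not a correction.

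The second reply is that leaving is already documented as a participation element. That also stands, and it limits the harm. It does not change the label, which is the only classification the rule produces.

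Three stronger readings are tempting and should be set aside:

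- **That the leaver has read 1 of 1 posts and passes the reading limb as well.** This is strained. The limb refers to the moderator's weekly series, which runs for six months, and nothing suggests cutting the series at departure. It is still worth stating the denominator.
- **That reported adherence would be inflated by some given number of percentage points.** Any such figure rests on invented reading and posting rates. It also treats everyone not labelled non-adherent as adherent, which the protocol never says for WhatsApp.
- **That the trial's main result is at risk.** Adherence is descriptive and has no threshold, and the return proportion is analysed as randomized regardless of compliance.

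**Conclusion.** The point holds as a minor defect of definition. By its own words the cut-off fails to flag a donor who posts three times in week 1 and leaves, and a donor who posts three times and reads nothing. That is out of step with the participation list beside it, with duration and dose as stated parts of adherence, and with the all-components rule used for the docu-drama. It is more than a missing detail, because a stated rule gives the wrong class to early leavers on a named feasibility measure.

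The direction is certain: the written rule flags no more donors than any reading in which a single failure counts. The size is unknown, and the early leaver is an example with no stated frequency. The conclusion rests on a literal reading of one sentence and on about 24 to 26 weekly posts; the choice within that range does not matter. The effect does not extend beyond the descriptive adherence result.

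**What to change.** Amend the cut-off under the 6 months heading as follows.

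1. Fix the reading denominator as all weekly moderator posts in the donor's own six months, with posts sent after departure counted as unread.
2. Class a donor who leaves before receiving half of those posts as non-adherent, whatever their post count. With 26 posts such a donor can have read at most 12/26 = 46%, so fails the reading limb anyway. The explicit clause is needed because, under the written rule, three posts would still remove the label.
3. Report three components separately as n/64 in the WhatsApp arm: stayed in the group, read at least 50%, posted at least three times.
4. Show the composite both as fails both and as fails either, so that the feasibility conclusion does not rest on the and/or choice. Silent readers, and donors who leave after the midpoint, then remain visible.
5. Record group join and leave dates in the moderator log. The Baseline B form gives only the randomization date, and eligibility allows donors who have yet to sign up for WhatsApp, so the joining date cannot be taken from the form.

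The cost is a short text change and at most 2 × 64 = 128 dates. The moderator already checks read status and posts, and no visit or participant is added. The downside is a somewhat less favourable adherence figure.
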